### 3. STUDY DESIGN

## 3.1. General Description

This is a multicenter, randomized, blinded, parallel group, interchangeability study in moderate to severe chronic plaque psoriasis evaluating PK, efficacy, safety, and immunogenicity between patients receiving Humira continuously and patients undergoing repeated switches between Humira and Hulio.

A study schema is provided in Table A – Study Diagram.

This study is planned to enroll 370 patients at approximately 36 study centers located in Europe. The total duration of the study for an individual patient who completes the study according to the protocol will be up to 32 weeks (inclusive of Screening and Follow-up safety assessment periods):

#### Screening Period:

Patients will be enrolled into the study after successfully completing screening activities between Day -21 to Day -1. Run-in Period:

Patients will receive Humira (initial dose of 80 mg [ $2 \times 40$  mg]; Day 1, Week 1) administered subcutaneously (SC), followed by 40 mg SC given every other week starting 1 week after the initial dose (last dose at Week 10/Visit 6).

Document: \\ieedc-vnasc01\Biosdata\Viatris\HULIO\HAB34991\Biostatistics\Documentation\SAP

Author: Version Number: 2.0

Version Date: 29Nov2023

Template No.: CS\_TP\_BS016 Revision 7 Reference: CS\_WI\_BS005

Page 13 of 48

Randomized Interchangeable Treatment Period:

Patients achieving at least a PASI 50 response at beginning of Week 12 /Visit 7 will be randomly assigned in a 1:1 ratio to either of the following groups for participation in the Randomized Interchangeable Treatment Period:

Group 1: Patients continue to receive Humira (40 mg every other week) until Week 26 /Visit 14.

Group 2: Patients undergo repeated switches until Week 26 /Visit 14:

- Hulio (40 mg every other week) for 4 weeks,
- Humira (40 mg every other week) for 4 weeks, and
- Hulio (40 mg every other week) for 8 weeks.

Randomization will be stratified based on Week 12/ Visit 7 PASI response:  $\geq$  PASI 50 to  $\leq$  PASI 75 or  $\geq$  PASI 75. Last dose in the Randomized Interchangeable Treatment Period will be at Week 26. Follow-up safety assessment will be done 4 weeks post last dose of study drug treatment received during the Randomized Interchangeable Treatment Period. The last efficacy and PK assessments are at start of Week 28/ Visit 15.

#### 3.2. Schedule of Events

Schedule of events can be found in Table 1: Study Schedule (Schedule of Assessment) of the protocol.

### 3.3. Changes to Analysis from Protocol

Not applicable.

### 4. SAMPLE SIZE DETERMINATION

Assuming a Mean Ratio (MR; switching arm vs non-switching arm) of 93.5% and a coefficient of variation (CV) of 38% for each of the PK parameters, AUC $\tau$  and Cmax and, also assuming independence between AUC $\tau$  and Cmax, an anticipated non evaluable rate of 15%, a sample size of approximately 330 participants (280 evaluable participants)

Document: \\ieedc-vnasc01\Biosdata\Viatris\HULIO\HAB34991\Biostatistics\Documentation\SAP

Author: Version Number: 2.0

Version Date: 29Nov2023

Template No.: CS\_TP\_BS016 Revision 7 Reference: CS\_WI\_BS005

Effective Date: 01Nov2021

Page 15 of 48

would provide 90% power to demonstrate that the 90% Confidence Intervals (CIs) for the MR are within 80.00% to 125.00% for both primary PK parameters. This study is planned to randomize 330 subjects, 165 subjects per treatment arm. To account for 10% Run-in failures, approximately 370 subjects will be enrolled into the study.

Here are the R program codes used for the sample size calculation: library(PowerTOST) sampleN.RatioF(CV = 0.38, theta0 = 0.935, targetpower= 0.9487, design='parallel', alpha=0.05) N=282 from the above R output.

Applicant's assumption of coefficient of variation (CV) of 38% was calculated from the published adalimumab interchangeability study (VOLTAIRE-X trial, https://clinicaltrials.gov/ct2/show/results/NCT03210259).

The residual CVs, which were calculated after covariates adjustment in the model, were approximately estimated from the above published study in three ways:

First, the reported 90.2% Confidence Intervals of AUCt & Cmax were used to calculate the CV using Fieller's theorem. This is the direct back-calculation using the Voltarie-X's SAP and their reported CIs. The CV was estimated at 37% for AUC and 36% for Cmax. The SAS program for AUC, and output for AUC are listed below as reference. SAS program:

data cv;

CIhigh=114.62; CIlow =96.58; /\* CI for AUC \*/ n1=102; n2=93; /\* N for AUC \*/

CIpercent=90.2; /\* as stated in BI report, 90.2% CI was reported \*/

alpha=0.5+CIpercent/100/2; t=tinv(alpha, n1+n2-2);

CVi = 0.367; /\* Initial CV value \*/

G=t\*\*2\*CVi\*\*2/N2;

ratio=(CIhigh/100 + CIlow/100)\*(1-g)/2;

sqrt=sqrt(1/N1\*(1-G)+ratio\*\*2/N2);

cv=(CIhigh/100\*(1-G)-ratio)/t/sqrt; /\* final CV \*/

drop CIpercent;

proc print data= CV;

run;

Document: \\ieedc-vnasc01\Biosdata\\Viatris\HULIO\HAB34991\Biostatistics\Documentation\SAP

Author: Version Number: 2.0

Version Date: 29Nov2023

Template No.: CS\_TP\_BS016 Revision 7 Reference: CS\_WI\_BS005

Page 16 of 48

SAS output:

```
Obs CIhigh CIlow n1 n2 alpha t CVi G ratio sqrt cv
1 114.62 96.58 102 93 0.951 1.66268 0.367 .004003738 1.05177 0.14717 0.36714
```

Secondly, the reported 90.2% Confidence Intervals of AUCt & Cmax were used to calculate the CV assuming that log transformation was used. This gave an approximate estimation with a clear limitation. The CV was estimated at 37% for AUC and 36% for Cmax. The SAS program for AUC, and output for AUC are listed below as reference. SAS program:

data intercv;

CIhigh=114.62; CIlow =96.58; /\* CI for AUC \*/

n1=102; n2=93; /\* N for AUC \*/

CIpercent=90.2; /\* as stated in BI report, 90.2% CI was reported \*/

t=0.5+CIpercent/100/2;

diff=log(CIhigh/100) - log(CIlow/100);

stdeest=diff/2/tinv(t,n1+n2-2);

sigma=stdeest/sqrt(1/n1+1/n2);

interCV=sqrt(exp(sigma\*\*2)-1)\*100;

proc print dat=interCV;

run;

sas output:

Obs CIhigh CIlow n1 n2 CIpercent t diff stdeest sigma interCV 1 114.62 96.58 102 93 90.2 0.951 0.17125 0.051498 0.35919 37.1087

Thirdly, the CV was back calculated using the sample size calculation formula description in Section 15 of the Boehringer Ingelheim (BI)'s SAP (Page 39 of 121) which resulted in a maximum CV (AUCt and Cmax) of 37%.

Here is the formula used by Boehringer Ingelheim (BI) in their SAP:

```
sampleN.RatioF(alpha=0.049, CV=, theta0=0.92, targetpower=0.8, design="parallel"),
```

Based on the VOLTAIRE-X trial information posted on clinicaltrial.gov, 102 & 93 patients from each arm was included in the final analysis. That is 195 subjects in total.

If it was assumed that the calculated N was 196, then the CV was estimated at 37% when BI performed Blinded

Document: \\ieedc-vnasc01\Biosdata\\Viatris\HULIO\HAB34991\Biostatistics\Documentation\SAP

Author: Version Number: 2.0

Version Date: 29Nov2023

Template No.: CS\_TP\_BS016 Revision 7 Reference: CS\_WI\_BS005

Page 17 of 48

Review of Sample size. It further validated the CV estimation.

### 5. PLANNED ANALYSES

The following analyses will be performed for this study:

Final Analysis

## **5.1.Data Monitoring Committee (DMC)**

There will be no DMC for this study.

### 5.2. Final Analysis

All final, planned analyses identified in this SAP will be performed by IQVIA Biostatistics for non-PK related items and Viatris Biostatistics for PK related items following Sponsor Authorization of this Statistical Analysis Plan, Database Lock, and Sponsor Authorization of Analysis Sets.

### 6. Analysis Populations

Agreement and authorization of patients included/excluded from each analysis set will be conducted prior to the unblinding of the study.

# 6.1.All Patient Screened [SCR] Population

The All Patient Screened (SCR) Population will contain all patients who provide informed consent for this study.

# 6.2.All Patient Enrolled [ENR] Population

The All Patient Enrolled (ENR) Population will contain all patients from SCR Population patients who meet eligibility criteria and enrolled into the study.

Document: \\ieedc-vnasc01\Biosdata\Viatris\HULIO\HAB34991\Biostatistics\Documentation\SAP

Author: Version Number: 2.0

Version Date: 29Nov2023

Template No.: CS\_TP\_BS016 Revision 7 Reference: CS\_WI\_BS005

Effective Date: 01Nov2021

Page 18 of 48

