- 8. Is positive for human immunodeficiency virus (HIV), hepatitis C virus antibody, or hepatitis B surface antigen (HbsAg) or is positive for hepatitis B core antibody at Screening
- 9. Has laboratory abnormalities, including but not limited to clinically significant hematological abnormalities, that, in the opinion of the PI or designee, could

	cause this study to be detrimental to the subject. The subjects should be excluded if they have the following laboratory abnormalities				
	a.	Hemoglobin <9 g/dL			
	b.	Platelet count <100 000/mm ³			
	c.	White blood cell count <3000 cells/mm ³			
	d.	Aspartate aminotransferase and/or alanine aminotransferase that is persistently $\geq 2.5 \times$ the upper limit of normal. (Persistently indicates elevated transaminases, at least on two separate occasions)			
	e.	Creatinine clearance <50 mL/min (Cockcroft-Gault formula)			
	I	re progressive or uncontrolled, clinically significant disease that in the of the PI or designee renders the subject unsuitable for the study			
	11. Has a history of malignancy within 5 years except for adequately treated cutaneous squamous or basal cell carcinoma, in situ cervical cancer, or in sit breast ductal carcinoma				
	12. Has an active neurological disease, such as multiple sclerosis, Guillain-Barré syndrome, optic neuritis, and transverse myelitis, or a history of neurologic symptoms suggestive of central nervous system demyelinating disease				
	13. Has moderate to severe heart failure (New York Heart Association [NYHA Class III/IV)				
	14. Has a history of hypersensitivity to the active substance or to ar excipients of Humira or Hulio				
	15. Is pregnant or nursing (lactating) woman				
	I	ence (as assessed by the PI or designee using good clinical judgment) l or drug abuse or dependency up to 5 years prior to Screening			
	I	to follow study instructions and comply with the protocol in the of the PI or designee.			
Planned Number of Subjects	evaluable participants) would provide 90% power to demonstrate that the 90% confidence intervals (CIs) for the MR are within 80.00% to 125.00% for both primary PK parameters.				
	This study is To account for into the study	or 10% run-in failures, approximately 370 subjects will be enrolled			
Statistical Methods	Analysis Set All Subject I this study.	: Enrolled population: All subjects who provide informed consent for			

Version 2.0

This information is confidential to Viatris.

Page 9 of 91

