## 6.3. Run-in Period Population [RPP]

The Run-in Period Population (RPP) will contain all enrolled patients who received at least one dose of Humira in the Run-in Period.

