### 6.4. Safety Population [SAF]

The safety population (SAF) will contain all patients who received at least one dose of randomized study medication (i.e., patients who received at least one dose of Humira in Group I or Hulio in Group II of the Randomized Interchangeable Treatment Period).

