## 6.5.Per Protocol Population [PPP]

The Per Protocol Population (PPP) will contain all randomized patients in the Safety population who have assessments prior to randomization and at least once post-randomization for at least one secondary efficacy endpoint and who do not have any important protocol violations impacting efficacy.

Reasons for exclusion can be, but not limited to:

Non-compliance with the inclusion or exclusion criteria.

Insufficient essential efficacy data for the secondary analysis.

Intake of prohibited medication.

Non-compliance with randomization criteria.

Non-compliance with the study treatment.

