## 10.1. Disposition

A clear accounting of the disposition of all patients who enter the study will be provided for the ENR, from enrolment to study completion. The patient disposition summaries include the following:

A summary of the number of screened patients, the number and percentage of screen failures and reasons for screen failure (Withdrawal by patient, Adverse Event, lost to follow up, Entry criteria not met, Sponsor decision, and Other), using the SCR population.

Document: \\ieedc-vnasc01\Biosdata\Viatris\HULIO\HAB34991\Biostatistics\Documentation\SAP

Author: Version Number: 2.0

Version Date: 29Nov2023

Template No.: CS\_TP\_BS016 Revision 7 Reference: CS\_WI\_BS005

remplate No.: OC\_11\_BOO10 Nevision /

Page 24 of 48

Patients entering the Run-in Period at Week 1, patients completed Run-in period, patients discontinued during the run-in period, reasons for not completing the Run-in Period, patients Run-in failed, patients completed the Run-in Period but not randomized, reasons for completed Run-in period but not randomized, patients randomized at Week 12, patients completed the full course of study treatment, patients discontinued treatment, reason for treatment discontinuation, patients completed the study, patients discontinued the study, reason for study discontinuation will be summarized by planned treatment group.

Additionally, separate tables for reasons for exclusion from each analysis population, including inclusion and exclusion criteria will be presented for the Enrolled population.

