#### 10.2. Protocol Deviations

Protocol deviations are the deviations from the procedure outlined in the protocol. All the Protocol Deviations (PDs) will be summarized using the Run-in period population as obtained from Clinical Trial Management System (CTMS) logs. PDs will be identified and discussed with the Investigator/Sponsor in PD review discussion to categorize them, and to finalize analysis population assignment.

Any PDs will be categorized into critical, major, and minor protocol deviations and will be summarized based on severity categories. An additional table summarizing the number and percentage of patients with Important PDs will be presented. Critical and Major protocol deviations having impact on primary analysis will be considered while finalizing the Per Protocol (PP) population. PDs log will be used for reporting purpose in tables.

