### 19. SAFETY OUTCOMES

All outputs for safety outcomes will be based on the Run-in period and SAF populations.

There will be no statistical comparisons between the treatment groups for safety data, unless otherwise specified with the relevant section.

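### SAP 6.2 makes eligibility a condition of the Enrolled population; if 6.3 takes *enrolled* from it, patients dosed in run-in in breach of a criterion drop out of run-in safety and deviation reporting

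*SAP*

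**What the plan says.** The Enrolled (ENR) population in SAP 6.2 "will contain all patients from SCR Population patients who meet eligibility criteria and enrolled into the study". It is drawn from the Screened (SCR) population of 6.1, which is everyone who gave consent. The Run-in Period Population (RPP) in 6.3 "will contain all enrolled patients who received at least one dose of Humira in the Run-in Period". The Safety population (SAF) in 6.4 "will contain all patients who received at least one dose of randomized study medication", with no condition on enrolment or eligibility.

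The outputs that depend on these sets are as follows.

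- SAP 19: "All outputs for safety outcomes will be based on the Run-in period and SAF populations". Section 19.1 assigns events from the first run-in dose up to the first randomised-period dose to RPP, and later events to SAF.
- SAP 10.2: "All the Protocol Deviations (PDs) will be summarized using the Run-in period population".
- SAP 10.1: separate tables of "reasons for exclusion from each analysis population, including inclusion and exclusion criteria will be presented for the Enrolled population".
- SAP 6.5 gives as one reason for leaving the per-protocol set: "Non-compliance with the inclusion or exclusion criteria".

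The protocol synopsis, under Statistical Methods, defines the set differently: "Enrolled population: All subjects who provide informed consent for" this study. Its Run-in population is then the enrolled subjects given at least one run-in dose of Humira. SAP 3.3 (Changes to Analysis from Protocol) reads *Not applicable*. The SAP modification history lists the Screened population as added and the Enrolled population as updated in version 2.0.

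**The concern.** Anyone who receives study drug should appear in the safety tables for the period in which it was given, whether or not an entry criterion was breached. An eligibility breach should appear in the deviation table. Read literally, 6.2 and 6.3 together prevent both: the breach removes the patient from the set on which the breach would be reported.

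At stake are the run-in safety summaries (adverse events, serious events, deaths) and the account of how well entry criteria were followed. Prior adalimumab is an exclusion criterion, so run-in is meant to be each patient's first exposure to the drug, including the initial dose. RPP is also the set for demographics, medical history, medications and run-in exposure (SAP 11, 12, 14 and 15), so the same patients would be missing there too.

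**Working it through.** The plan gives no figure on this point, so there is nothing to reproduce. The check is one of set membership.

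**Definitions.** Take a consented patient. Let E = meets the eligibility criteria, N = entered into the study, H = at least one run-in Humira dose, R = at least one randomised-period dose.

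- ENR as written (SAP 6.2) = E and N.
- RPP if *enrolled* means ENR (6.3 read with 6.2) = E and N and H.
- RPP if *enrolled* means only entered = N and H.
- RPP in the protocol = consent and H.
- SAF (6.4) = R.

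**Membership of patients dosed in run-in (N and H both true).**

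| Patient | ENR as written | RPP, linked to 6.2 | RPP, looser reading | RPP, protocol | SAF |
|---|---|---|---|---|---|
| Meets criteria, not randomised | yes | yes | yes | yes | no |
| Breaches a criterion, not randomised | no | **no** | yes | yes | no |
| Breaches a criterion, randomised and dosed | no | **no** | yes | yes | yes |

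**Consequences on the linked reading.**

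1. *Breach, not randomised.* The patient is in neither RPP nor SAF. Section 19 bases all safety outputs on those two sets, so no event in this patient is reported.
2. *Breach, randomised.* The patient is in SAF, but 19.1 places in SAF only events that start or worsen from the first randomised-period dose. Run-in events belong to RPP, where the patient is absent.
3. *Deviations.* All summaries use RPP (10.2), so both kinds of patient, with their eligibility deviations, are missing.
4. *Disposition.* Section 10 undertakes to account for everyone who consents, and 10.1 reports screen failures on SCR and the remaining flow for ENR. A patient who was entered and dosed in breach was not a screen failure, yet is not in ENR.

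**Consistency with the rest of the SAP.** Section 6.5 removes eligibility violators from the per-protocol set, so it expects some to have been dosed. Section 10.1 tabulates inclusion and exclusion criteria as exclusion reasons within ENR. If ENR holds only patients who meet the criteria, those rows must be zero.

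**Consistency with the protocol.** The SAP's SCR set now has the definition that the protocol gives to Enrolled. RPP kept almost the same sentence while the term it rests on was narrowed. Under the protocol, consent plus a dose is enough, so all three rows of the table are in RPP. Section 3.3 does not record the difference.

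**What does not change.** SAF and the PK population (6.6) carry no ENR condition, and the per-protocol set (6.5) is drawn from SAF. The primary PK analysis, the secondary efficacy analyses and randomised-period safety are the same on either reading.

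**The case against.** The strongest reply is that 6.3 does not name ENR. Where this SAP builds one set from another it usually names the parent: 6.2 names SCR and 6.5 names the Safety population. Section 6.3 says only that patients are enrolled. In addition, 3.1 describes enrolment as following successful screening, and 10.1 reports unmet entry criteria as a screen-failure reason on SCR. Since SCR was added and ENR updated in the same SAP version, 6.2 may be meant only to separate screen failures from patients who entered. On that reading a dosed violator stays in ENR and RPP, and the 10.1 tables make sense. Sections 6 and 10.2 also provide for agreement on set membership before unblinding and for a deviation review, which makes an unnoticed loss less likely.

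Much of this stands. The loss depends on the link between 6.2 and 6.3, and the looser reading is reasonable and may be the intended one. But the SAP does not state it, 6.2 is the only definition of the enrolled population, and it stands directly above 6.3. Two programmers could build different run-in safety tables from this text. A membership review applies the definitions; it does not rewrite them.

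A reader might infer three stronger things that the documents do not support.

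- *A count of lost patients.* Assumed breach rates of 1% and 5% of the 370 planned would give 0.01 × 370 = 3.7 and 0.05 × 370 = 18.5 patients. No rate is given, and the group lost from every safety set is only those who breach a criterion and also stop before randomisation.
- *That the omitted patients are those most likely to have events.* Nothing in the documents shows this. Some exclusions concern safety (active infection, heart failure), but others concern disease severity, stability or topical washout.
- *That run-in data on violators will certainly be lost, or that eligibility compliance will certainly look perfect.* Both follow only on the linked reading.

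**Conclusion.** The point holds as a conditional defect in the definitions. If *enrolled* in 6.3 has the meaning given in 6.2, patients dosed in run-in in breach of a criterion are missing from run-in safety outputs and all deviation summaries, and those never randomised are in no safety set. The conflict with 6.5 and 10.1 suggests a drafting slip, but it does not remove the rule as written. Separately, and on either reading of 6.3, the Enrolled definition departs from the protocol's consent-based one without being declared in 3.3.

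The number of patients affected cannot be derived from the documents and could be zero. The effect is confined to descriptive outputs: run-in safety, deviations, disposition and the other RPP tables. No confirmatory result, power or type I error is touched. It should be corrected because the ambiguity concerns who is counted in safety reporting and costs almost nothing to remove.

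**What to change.** 1. In SAP 6.3, define RPP as all patients who received at least one dose of Humira in the run-in period, regardless of any breach of an inclusion or exclusion criterion. This alone secures run-in safety and deviation reporting.
2. In SAP 6.2, delete the eligibility condition, so that ENR is all SCR patients entered into the study. The 10.1 tables can then show eligibility breaches.
3. In SAP 3.3, record that ENR still differs from the protocol's Enrolled population, which is everyone who consented and corresponds to the SAP's SCR.

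Eligibility violators can still be removed from the per-protocol set under 6.5, and the PK population rules in 6.6 are unchanged. The cost is a few sentences and no new data. The deviation tables may look slightly less favourable.

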## 6.3. Run-in Period Population [RPP]

The Run-in Period Population (RPP) will contain all enrolled patients who received at least one dose of Humira in the Run-in Period.

